7.3 Primary endpoint analysis

We will model the main intervention effect for each randomisation separately. For both, we will use a binomial Generalized Estimating Equation (GEE) model with identity link and a log link function to estimate adjusted risk difference and adjusted risk ratio (in line with CONSORT reporting recommendations) with robust variance. This will enable us to account for within network correlations. Intervention effect for the first and second randomisation will be modelled separately. Both models will be adjusted for minimisation variables.

The analysis model for randomisation 1 will include whether or not an infant received fortification (Y/N) and whether or not they were randomised to this (randomisation 2; Y/N)). Though randomisation 2 will occur after randomisation 1, they are close in time and receiving fortification may be more likely to be a predictor of the primary outcome than a result of taking part in randomisation 1. Therefore, randomisation 2 and receipt of fortification will be treated as baseline covariates.

The analysis model for randomisation 2 will include adjustment for taking part in randomisation 1 (Y/N) and type of supplementary feed received (pHDM or formula). A supplementary analysis for randomisation 2 will be performed to determine the effect of rescue fortification in the standard of care arm (no routine fortification) will be undertake using principal stratum and complier average causal effect approaches (no rescue fortification is defined as a complier in the standard of care arm). In the unlikely case that missing data are greater than 2%, a sensitivity analysis will be performed using multiple imputation.

Title: COLLABORATE	EDGE No: 181495	Sponsor: Imperial College London	Version: 3.0; 09/01/2026
---------------------------	---------------------------	--	---------------------------------

Binary secondary and key safety outcomes (death, surgical NEC, medical NEC, infection) will be analysed using the same principled approach as the primary outcome. The age 2-year PARCA-R will also be evaluated as a continuous outcome and the between arm mean difference estimated using the GEE model with normal distribution and identity link function adjusting for minimisation variables.

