5.3.2 Method

Randomisation will be carried out electronically using an on-line system managed by the ICTU Clinical Data Systems Team. We will use minimisation (with 10% random allocation) to achieve

Title: COLLABORATE	EDGE No: 181495	Sponsor: Imperial College London	Version: 3.0; 09/01/2026
---------------------------	---------------------------	--	---------------------------------

balance between the number of babies in each treatment group over important, well-recognised prognostic factors [neonatal network (N=13); gestational age category (<26w; >=26w); severe growth restriction (<10% centile; >=10% centile based on standard criteria)]. Multiple births will be randomised individually in keeping with our feasibility study (12), other feeding trials (28), and parent focus group advice.

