7.2 Sample size and power

7.2.1 Main study

This is a group-sequential trial with 2 interim and 1 final analysis (i.e., an adaptive trial), hence the sample size is not fixed. The maximum sample size is 3252, (n=2168 in each randomisation; n=1084 per arm) assuming no early stopping, estimated on the composite primary efficacy outcome (survival to 34 weeks gestational age without surgical NEC (Y/N)).

Title: COLLABORATE	EDGE No: 181495	Sponsor: Imperial College London	Version: 3.0; 09/01/2026
---------------------------	---------------------------	--	---------------------------------

For the randomisation 1 (pHDM vs Formula supplement) an observational analysis of NNRD data estimated the difference in the proportion surviving to 34w PMA for babies born <29 weeks' gestation to vary between 0.18 and 0.52 depending on week of gestational age (favouring supplementation with preterm formula) (6) For the sample size calculation we targeted a highly conservative MCID in this proportion of 0.05 based on a baseline of 0.82 which we accurately estimated from the NNRD for this population of babies in the UK (i.e. from 0.82 to 0.87).

For randomisation, 2 (fortifier vs no routine fortifier) an unpublished observational analysis from NNRD data estimated the difference in proportion data surviving to 34w PMA for babies born <29 weeks gestation to vary between 0.06 and 0.75 depending on week of gestational age (favouring fortifier). Taking a conservative approach and in line with the first comparison, we have chosen to target the same MCID of 0.05.

We have calculated power based on a fixed sample size of 3252 unique babies using rpact (33) where interim timings were chosen to minimise the expected sample size. We anticipate at least 50% of babies will be co-enrolled into both randomisations. If co-enrolment is higher, power will increase. We have used an O'Brien & Fleming design with two-sided overall significance level of 5% to account for two interims at 50% and 75% and a normal approximation assumption for rates. For both randomisations we have factored in 2% missing outcome data due to carers withdrawing consent from routine data collection in NNRD.

Based on all the above assumptions, n=3252 (n=2168 in each randomisation and n= 1084 per arm) will achieve a minimum of 87% power for each randomisation. The expected sample size across for each randomisation is n=2439.

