7.4 Interim assessment of efficacy

We will conduct two pre-planned formal interim efficacy analyses when 50% and 75% of participants reach 34 weeks gestational age (i.e., primary outcome is available). This analysis will be undertaken by an independent ICTU statistician. Recruitment will continue during interim analyses. The analysis will employ two-sided O'Brien-Fleming efficacy boundaries. Unadjusted between arm differences in proportions will be calculated using the primary analysis models described for the final analysis. An identify link function will be used to obtain adjusted risk differences and corresponding Z-scores. Superiority will be assessed at each stage based on the critical value thresholds (Z-scores) and numbers of participants.

Proportion recruited	50%	75%	100%
Randomisation 1, n	954	1431	1908
Randomisation 2, n	1063	1594	2126
Critical value thresholds (Z-scale)	2.863	2.337	2.024

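### Read literally, the randomisation 1 model enters network as both cluster and 13-level covariate under identity and log links; in most simulated first interims it has no valid fit, and 7.4 leaves open whether the stopping Z-score depends on it

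*Protocol*

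**What the plan says.** Protocol 7.3 fixes the family and links of the primary model: "we will use a binomial Generalized Estimating Equation (GEE) model with identity link and a log link function", with robust variance, for the adjusted risk difference and risk ratio. It gives the reason for the GEE as "This will enable us to account for within network correlations" and adds "Both models will be adjusted for minimisation variables". Section 5.3.2 lists those variables, beginning "neonatal network (N=13); gestational age category (<26w; >=26w", followed by severe growth restriction. No exception is made for network.

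For randomisation 1 there are two further terms: "The analysis model for randomisation 1 will include whether or not an infant received fortification (Y/N") and whether the infant entered randomisation 2.

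On the interim analyses, 7.4 says "Unadjusted between arm differences in proportions will be calculated using the primary analysis models described for the final analysis". The next sentence says "An identify link function will be used to obtain adjusted risk differences and corresponding Z-scores". The critical values are 2.863, 2.337 and 2.024, at n = 954, 1431 and 1908 for randomisation 1.

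**The concern.** Identity and log links do not keep fitted survival probabilities below 1. That is tolerable with few covariates or mid-range risks. Here survival is expected at 0.82 to 0.87, and the literal randomisation 1 model has 1 intercept + 1 arm + 12 network + 1 gestation + 1 growth + 2 fortification = 18 mean parameters on 13 clusters. A baby with every favourable characteristic in a favourable network can easily get a fitted survival above 1. The binomial variance is negative there, so it is not a valid fit.

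Two things are at stake. One is the reported adjusted risk difference and risk ratio. The other, if the adjusted reading of 7.4 is meant, is the Z-score that can stop randomisation 1. The failure need not be visible, because software may print a Z-score from a fit that did not converge.

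**Working it through.** **The plan's own figures.** With looks at 50%, 75% and 100%, the three boundaries give a two-sided alpha of 0.050. Group-sequential power for 0.82 v 0.87 is 89.0% at n = 2168 and 88.4% at n = 2126 (about 2% missing), within 2 points of the stated minimum of 87%. The boundaries are sound; the question is which Z-score is compared with them.

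**Inputs from the protocol.** Failure 15.5%, the mean of 0.18 and 0.13 (7.2.1). Sample sizes from 7.4. About half of babies fortified (1.4). Half of babies in both randomisations (7.2.1). Fortification difference of 0 points (floor), 6 points and 15.1 points. The 6 points is the lowest value in 7.2.1, where the difference is said "to vary between 0.06 and 0.75 depending on week of gestational age (favouring fortifier"). The 15.1 points (1.5.3) comes from a broader very preterm group and is an upper case. At 15.5% failure, 6 points is 12.5% v 18.5%, OR (0.125/0.875)/(0.185/0.815) = 0.63; 15.1 points is 7.95% v 23.05%, OR 0.29.

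**Assumed, because the protocol gives no figures.** 13 equal networks (SD 0.2 on the logit scale), 35% below 26 weeks (OR 2.5), 15% growth-restricted (OR 1.8).

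**Why it fails: rough arithmetic, first interim, 6-point case, 5-point effect.** There are 954/13 = 73 babies per network, so a network's failure rate has standard error √(0.155 × 0.845/73.4) = 4.2 points. The lowest of 13 such estimates lies about 1.67 standard errors, or 7.0 points, below average. Babies at 26 weeks or more fail at 11.1%, which is 4.4 points below average. The best pattern is then 15.5 − 2.5 (arm) − 3.0 (fortified) − 4.4 (gestation) − 7.0 (network) = −1.4% failure, that is, survival above 1.

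**Criterion.** Under independence working correlation the GEE score is the Bernoulli score. Its log-likelihood is concave under the identity link, so any valid root is the unique maximum. A trial counts as having no valid fit if that root puts an observed covariate pattern outside 0-1. This agreed with a constrained optimiser in 25 of 25 trials.

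**Share of simulated randomisation 1 trials with no valid identity-link fit** (fortification difference 0 / 6 / 15.1 points; ranges span those three cases):

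| Model | n=954 | n=1431 | n=1908 |
|---|---|---|---|
| Literal, no treatment effect | 63/80/99% | 28/58/96% | 13/41/90% |
| Literal, 0.82 v 0.87 | 75/92/100% | 53/77/99% | 32/63/98% |
| Minimisation variables only (network indicators, no fortification terms), no effect | 30-33% | – | 2-4% |
| Same, 0.82 v 0.87 | 48-56% | – | 12-15% |
| Network as cluster only, fortification terms kept, no effect | 0/0/7% | – | 0-1% |
| Same, 0.82 v 0.87 | 0/1/15% | – | 0-1% |

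There were 1000 replicates per cell without and 500 with the effect (Monte Carlo SE at most 1.6 and 2.2 points). A logistic model on the literal covariates failed in 0-0.1%. The log link on survival, literal and without effect, failed in 77/91/99% at n = 954 and 18/46/91% at n = 1908 (300 replicates).

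**Sensitivity.** Repeating the literal no-effect case with fresh code gave 67/81/99% at n = 954 and 15/46/88% at n = 1908. Varying the gestation OR (2-4), network SD (0-0.3) or network sizes (up to 1:3) gave 50-85% at n = 954 and 5-33% at n = 1908 for 0 points, and 70-95% and 26-64% for 6 points. With weak prognostic effects and no fortification or network effect, the shares at the three looks were 40/10/4%.

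**Software.** In 250 trials (n = 954, 6 points, 5-point effect), 231 had no valid solution. Default statsmodels GEE converged in none of the 231 but printed a finite Z-score in 99%.

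**The case against.** The strongest reply is that network is meant as the cluster only, with gestation and growth as the adjusting terms. The stated reason for using GEE supports that, and the failure rates above are then close to nil. This stands, and it means a reader may not conclude that the protocol certainly prescribes an unusable model. The cluster-only reading is not wholly safe: with effects generated additively, a 15.1-point fortification association and the strongest other effects tried, failure reached 51/42/28% at the three looks.

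The second reply is that model-building detail belongs in the statistical analysis plan, which is promised before the first interim. That is right for a convergence fallback or the working correlation. It does not answer this point: the protocol itself fixes the links, distribution, clustering and covariates, and 7.4 contradicts itself.

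The third is that the prognostic effects are assumed and the fortification differences observational. Section 1.5.3 admits possible residual confounding, and random allocation in randomisation 2 should weaken the association. That stands, so the 0-point column is the floor.

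Three stronger inferences are tempting but unsupported.
- **That the identity-link estimate is inherently far noisier.** In the default software run its risk difference had SD 3.9 points, against 2.1 for standardised logistic, but that reflects one package without convergence. With fitted risks bounded in the variance function all fits converged and the SD was 2.2 against 2.3, although the robust standard error was then too small (1.7).
- **That the trouble is confined to the interims.** With a 15.1-point association it persists at the final analysis.
- **That randomisation 2 or the binary safety outcomes fail likewise.** They share the approach but were not simulated.

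**Conclusion.** The point holds, conditionally. On the literal reading of 7.3 with 5.3.2, most simulated randomisation 1 trials have no valid identity-link fit at the first interim (63-99% without a treatment effect across fortification differences of 0 to 15.1 points). At the final analysis the share is 13-90%. On the cluster-only reading it is 0-1% for differences of 0-6 points, and 7-15% at the first interim if the association is as strong as 15.1 points.

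The sizes rest on assumed prevalences and effects of gestation, growth and network. The direction does not depend on the exact values: even the weakest case gave 40% at the first interim.

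A reader might infer that the stopping rule is broken. The text does not establish that. If the interim Z-score is unadjusted it always exists, and only the reported adjusted risk difference and risk ratio are affected. The contradiction in 7.4 is real whatever the simulation shows. This should be corrected before the first interim.

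**What to change.** **Preferred.** In 7.3 and 7.4, obtain the adjusted risk difference, risk ratio and any adjusted interim Z-score by marginal standardisation from a logistic model with the chosen covariates and cluster-appropriate variance.

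**Minimum.** State that network enters once only, as the GEE cluster, and not as a 13-level covariate in the identity- and log-link models. This leaves the 7-15% first-interim risk under the strong fortification association. An identity-link GEE with Gaussian variance is another workable route: with network as cluster and the minimisation covariates only, it converged in 60 of 60 simulated data sets at both n = 954 and n = 1908.

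**In either case.** Correct 7.4 to say whether the unadjusted or the adjusted Z-score is compared with 2.863, 2.337 and 2.024. Check randomisation 2 and the binary safety outcomes before extending the same model to them.

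**Cost.** Wording and slight programming; no new data. The standardised difference is a marginal effect and equals the identity-link coefficient only if the additive model holds. In the 250-trial run (effects additive on the logit scale, true difference 5 points), standardised logistic averaged 5.3 points, the unadjusted difference 5.3, and the identity link with network as cluster only 4.6.

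### With only 13 networks as clusters, an uncorrected robust GEE variance tested against normal O'Brien-Fleming limits gives an overall type I error of about 9-12%, not the stated 5%

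*Protocol*

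**What the plan says.** Four statements in the protocol combine here.

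- Section 7.3 fits a binomial GEE for each randomisation "to estimate adjusted risk difference and adjusted risk ratio (in line with CONSORT reporting recommendations) with robust variance", and gives the reason: "This will enable us to account for within network correlations". The natural reading is that network is the GEE cluster. The section adds: "Both models will be adjusted for minimisation variables".
- Section 5.3.2 lists the first minimisation variable as "neonatal network (N=13" and allocates individual babies, multiples included.
- Section 7.2.1 sets the error rate: "We have used an O'Brien & Fleming design with two-sided overall significance level of 5% to account for two interims at 50% and 75" per cent, under a normal approximation.
- Section 7.4 applies the final-analysis models at the interims and tabulates "Critical value thresholds (Z-scale) 2.863 2.337 2.024". The decision rule is: "Superiority will be assessed at each stage based on the critical value thresholds (Z-scores) and numbers of participants".

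The protocol mentions no small-sample variance correction and no t reference distribution.

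**The concern.** The accuracy of a sandwich variance depends on the number of clusters, not the number of babies. With 13 clusters the ordinary estimator is biased low and noisy, so the ratio of estimate to standard error has heavier tails than a standard normal. O'Brien-Fleming limits sit far out in the tail, where a t on about 12 degrees of freedom and a normal differ most in relative terms.

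The 5% overall error rate of both primary comparisons is at stake, as are the widths of their confidence intervals. Section 7.3 extends the same approach to the binary secondary and key safety outcomes, so their intervals are affected too.

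**Working it through.** **Inputs from the protocol.** Looks at 50%, 75% and 100%; limits 2.863, 2.337 and 2.024; overall two-sided 5% (7.2.1, 7.4). Thirteen networks; individual minimisation with a 10% random element (5.3.2). Analysed numbers at the three looks of 954/1431/1908 (randomisation 1) and 1063/1594/2126 (randomisation 2) (7.4). Event rates 0.82 and 0.87 (7.2.1), so the null was simulated at their midpoint, 0.845.

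**Assumed, because the protocol does not give them.** Network sizes (equal, or about a 7-fold range), ICC (0, 0.01, 0.03) and covariate effects.

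**Step 1: reproduce the plan's own figure.** The O'Brien-Fleming form is c/√t with c = 2.024: 2.024/√0.5 = 2.862, 2.024/√0.75 = 2.337, 2.024/√1 = 2.024. These match the table up to rounding. For a trivariate normal with correlations √(t_i/t_j), the probability that any |Z| exceeds its limit is 0.050. The limits are therefore right for a truly normal Z, and any excess comes from the statistic.

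**Step 2: closed-form approximation.** Suppose the uncorrected variance averages 12/13 of the true value and the studentised estimate follows a t on 12 df. Exceeding a limit b then means |t12| > b × √(12/13) = 0.9608 × b.

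| Look | Limit | 0.9608 × limit | Normal tail | t12 tail | Excess (points) | Ratio |
|---|---|---|---|---|---|---|
| 50% | 2.863 | 2.751 | 0.42% | 1.76% | 1.3 | 4.2 |
| 75% | 2.337 | 2.245 | 1.94% | 4.44% | 2.5 | 2.3 |
| 100% | 2.024 | 1.945 | 4.30% | 7.56% | 3.3 | 1.8 |

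The excess is largest at the first look as a ratio, and smallest there in absolute terms.

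For intervals, the same approximation calls for a multiplier of 2.179 × √(13/12) = 2.268 in place of 1.96. An uncorrected 95% interval would thus need to be about 16% wider (2.268/1.96 = 1.157).

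**Step 3: simulation of the full three-look rule under the null.** Adjusted for gestation and growth restriction, ICC 0.01, identity-link linear model, 15,000 trials per row (Monte Carlo standard error about 0.25 points). Adding network fixed effects changed the overall figure by no more than 0.05 points.

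| Setting | Uncorrected network sandwich, overall | By look | Model-based variance with network fixed effects | 13/12 factor and t12 reference |
|---|---|---|---|---|
| n=2126, equal networks | 9.8% | 1.9 / 4.6 / 7.6% | 4.9% | 5.2% |
| n=2126, unequal | 10.7% | 2.3 / 4.9 / 8.0% | 4.8% | 5.6% |
| n=1908, unequal | 11.3% | 2.1 / 5.2 / 8.7% | 5.1% | 6.1% |

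Over ICC 0 to 0.03, both size patterns and both sample sizes, the uncorrected figure ran from 9.1% to 11.6%. It hardly depends on ICC, because babies are randomised within network.

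**Step 4: check with a fitted binomial identity-link GEE** (exchangeable; blocks within network in place of minimisation). Uncorrected: 9.4% with equal networks (2,857 trials) and 11.6% with unequal (2,400 trials). Mancl-DeRouen variance against the normal limits: 7.0% and 8.5%. Mancl-DeRouen variance with a t12 reference: 4.5% and 5.5%. Correcting the variance alone is therefore not enough; the reference distribution must change as well.

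**Step 5: individual-level robust variance.** With network fixed effects and the same limits, overall error was 4.8% to 5.5% across separate sets of simulations.

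**The case against.** The strongest reply is that the protocol says only that the variance is robust. It does not say uncorrected. Mancl-DeRouen and Kauermann-Carroll variances are also robust, such detail is commonly left to the SAP, and section 7.1 promises a SAP before the first interim. A t-based p-value converted to Z is compatible with the table in 7.4. This stands as a limit on the claim: the 9-12% is conditional on the ordinary uncorrected sandwich. It does not remove the point, because the protocol itself fixes network-level correlation, 13 networks, Z-scale limits and a 5% claim. Taken with the usual estimator, these do not agree.

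A reader might infer three stronger things that the documents do not support.

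- *That correlation between siblings goes unhandled.* Section 5.3.2 says "Multiple births will be randomised individually in keeping with our feasibility study", and 7.3 names no sibling cluster. But a sandwich clustered on network already allows any correlation within a network, including between siblings cared for in the same one.
- *That the robust covariance matrix is rank-deficient and the test therefore invalid.* This depends on network entering as fixed effects, which 7.3 implies but does not spell out. It would not by itself invalidate the standard error of the treatment effect, and the inflation is the same with or without those effects.
- *That the damage is concentrated at the first interim.* This is true only as a ratio. Nor does the protocol make crossing a limit an automatic stop: sections 7.11 and 10.3 leave procedures to the committee charter and have the data monitoring committee advise the steering committee.

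Section 7.4 also calls the interim estimates both unadjusted and adjusted, so the adjusted interim model simulated here is one reading.

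**Conclusion.** The point holds. As written, and with the ordinary uncorrected sandwich clustered on 13 networks, the stated limits give an overall two-sided type I error of about 9-12% for each randomisation instead of 5%. First-look rejection is about 2% against 0.42%. Confidence intervals are too narrow, by roughly the 16% in the approximation above.

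The size rests on that choice of estimator and on assumed network sizes, ICC and covariate effects. The direction and rough size were stable over the range tried. The additional feeding covariates in 7.3 were not simulated. It would go too far to say that the trial will be tested at 10%, since an SAP that is not shown could still correct this.

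**What to change.** State one of these in section 7.3 and carry it into 7.4.

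(a) Keep network as a fixed categorical covariate and cluster the robust variance on mother or pregnancy. This gives many small clusters and still covers individually randomised multiples. The figure of about 5% was shown for individual-level robust and model-based variance with network fixed effects; mother-level clustering itself was not simulated.

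(b) Keep network as the cluster, with a small-sample corrected variance (for example Mancl-DeRouen or Kauermann-Carroll) and a t reference on about 12 df, converted to the Z or p-value scale before comparison with the limits. Type I error is then about 4.5-6%. On the t12 scale the three limits correspond to about 3.52, 2.70 and 2.26.

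Apply the same rule at both interims, at the final analysis, and to the secondary and safety outcomes analysed by this approach.

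The cost is a sentence or two in the protocol and SAP, somewhat wider intervals than the uncorrected method gives and, for (a), a mother identifier in the data extract. Option (b) also costs some power, which should be checked against the stated 87%. Allocation and the tabulated Z limits need not change. The choice should be settled before the first interim.

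### The primary models adjust for gestational age only as below 26 weeks or 26 weeks and over, although it is recorded more finely, and so give up a small amount of precision

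*Protocol*

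**What the plan says.** Section 7.3 specifies a binomial GEE for each randomisation, with an identity link for the risk difference and a log link for the risk ratio. It then states: "Both models will be adjusted for minimisation variables". Section 5.3.2 lists those variables as neonatal network, "gestational age category (<26w; >=26w") and growth restriction at the 10th centile. It describes them together as important and well-recognised prognostic factors and does not rank them.

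The same adjustment carries into other analyses. Section 7.4 takes the interim Z-scores from the primary models. Section 7.3 applies the same approach to binary secondary and key safety outcomes, and adjusts the two-year PARCA-R score for the minimisation variables.

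Three places show that gestation is available in finer detail:
- Section 7.2.1 reports earlier NNRD results by week of gestation for both comparisons.
- Section 7.5 cuts the subgroups at 26 weeks or less versus more than 26 weeks. That cut cannot be derived from the minimisation classes.
- Section 7.8 adjusts the MRI model for gestational age at birth and names no cut-point.

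**The concern.** Minimisation needs coarse classes; a regression model does not. If the chance of survival without surgical NEC differs by week within 22 to 25 or within 26 to 28 weeks, the two-level term cannot explain that variation, and chance imbalance by week inside a class goes uncorrected. The result is a somewhat wider confidence interval than the trial's own data would allow. Because the primary model is reused, the same loss recurs at the interim looks and in the secondary outcomes. What is at stake is efficiency only: an unbiased comparison that is slightly less precise than it could be.

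**Working it through.** **1. The plan's own power.** Inputs from sections 7.2.1 and 7.4: rates 0.82 and 0.87 ("we targeted a highly conservative MCID in this proportion of 0.05 based on a baseline of 0.82"); "n=2168 in each randomisation and n= 1084 per arm"; "factored in 2% missing outcome data"; looks at 50%, 75% and 100% with limits 2.863, 2.337 and 2.024.

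- Babies with an outcome per arm: 1084 × 0.98 = 1062.
- Variance term: 0.82 × 0.18 + 0.87 × 0.13 = 0.2607.
- Standard error: √(0.2607/1062) = 0.01567. Standardised effect: 0.05/0.01567 = 3.19.
- Fixed-design power: Φ(3.19 − 1.96) = 89.1%.
- Three-look power by simulation (2,000,000 draws): 88.5% with unpooled variance, 88.3% with pooled. Overall two-sided alpha: 0.0498.

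This agrees with the stated minimum of 87%. No covariate enters the calculation, so the stated power does not depend on how gestation is coded.

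**2. Gain from using weeks.** The week-specific outcome rates and the share of babies in each week are not in the protocol and are assumed here:

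- shares of 2, 8, 13, 15, 17, 21 and 24% for weeks 22 to 28;
- mean outcome 0.845, midway between 0.82 and 0.87;
- a logistic slope of 0.2 to 0.6 per week.

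The variance of the risk difference is taken as proportional to 1 − R², where R² is the share of outcome variance explained by gestation. The variance ratio is (1 − R² weeks)/(1 − R² two classes). Babies saved are 2168 × (1 − ratio). Power is recomputed with the standardised effect divided by √(1 − R²).

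| Slope | Assumed rate, 22 wk to 28 wk | R² two classes | R² weeks | Variance ratio | Babies of 2168 | Power, two classes to weeks |
|---|---|---|---|---|---|---|
| 0.2 | 0.72 to 0.90 | 0.0121 | 0.0162 | 0.9958 | 9 | 88.8 to 89.0% |
| 0.4 | 0.57 to 0.94 | 0.0472 | 0.0652 | 0.9811 | 41 | 89.9 to 90.4% |
| 0.6 | 0.42 to 0.96 | 0.0958 | 0.1379 | 0.9534 | 101 | 91.4 to 92.6% |

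For the middle row: (1 − 0.0652)/(1 − 0.0472) = 0.9348/0.9528 = 0.9811, and 2168 × 0.0189 = 41. As effective sample size the gains are 1/0.9958 − 1 = 0.4%, 1/0.9811 − 1 = 1.9% and 1/0.9534 − 1 = 4.9%. The two classes already capture about 70% to 75% of what weeks explain (0.0958/0.1379 = 69%; 0.0121/0.0162 = 75%).

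**3. A second pair of assumed gradients.**

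- Steep, 0.35 at 22 weeks to 0.94 at 28: R² of 9.4% against 13.5%, ratio 0.906/0.865 = 1.047 (1.043 when the trials are simulated).
- Flatter, 0.55 to 0.91: R² of 4.0% against 5.4%, about 1.4%.

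Applied to the unadjusted power, these ratios move it from 88.5% to 88.9–89.8% at about 2125 babies. At 1908, the smaller full-recruitment figure that section 7.4 gives for randomisation 1, they move it from 84.9% to 85.4–86.5%. The largest step is therefore 86.5 − 84.9 = 1.6 points.

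**4. Does a week term fit under the identity link?** With week entered linearly, the fitted probability at 28 weeks in the better arm (adding half the effect, 0.025) is 0.98 at slope 0.4, 1.00 at slope 0.5 and 1.03 at slope 0.6. The term can reach or pass the boundary in the steeper scenarios, which are also those where it gains most.

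**The case against.** The strongest reply is that nothing here is wrong. Adjusting for the factors used in allocation is valid and conventional. The protocol excludes no finer term, and the covariate form could be settled in the SAP that section 7.1 promises before the first interim. The two-level factor also has a practical merit: it is less likely to break an identity-link fit. All of that stands, and it is why the point concerns efficiency alone. It does not remove the point, because section 7.3 names the covariate set and, read with section 5.3.2, gives gestation two levels.

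The assumed gains may also be generous. The R² values are for gestation alone, with no allowance for growth centile, network and feed covariates already in the model. In randomisation 2 a baby must first reach the feed volume in section 5.3.1, so earlier deaths never enter, which would tend to flatten the gradient.

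Three stronger readings are tempting and not supported:
- **That gestation is the strongest predictor.** The protocol calls the minimisation factors important but does not rank them.
- **That section 7.2.1 shows the outcome gradient by week.** The figures said "to vary between 0.18 and 0.52 depending on week of gestational age" are differences between feeding groups in observational data, which section 1.5.2 says may be confounded. They are not outcome rates by week.
- **That the finer term costs nothing.** Step 4 shows that it may not fit as specified.

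**Conclusion.** The point holds as a minor matter of efficiency. As written, the primary models reduce gestational age to two classes although finer data are held. Under assumed week-specific rates the loss is about 0.4% to 5% of effective sample size (1.9% at the middle slope), roughly 10 to 100 babies per randomisation, or 0.1 to 1.6 points of power. The upper ends need a steep gradient that the protocol neither gives nor rules out. A reader might infer that the trial is underpowered or its comparison biased because of this coding. Neither follows: the 87% is reproduced with no adjustment at all, and a two-level covariate remains valid. The shortfall at 1908 babies comes from the smaller number; the coding of gestation neither causes nor cures it.

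**What to change.** Keep all the minimisation factors, including the two-level gestation class, and add gestational age in weeks as week categories or a spline, with the form fixed in advance. Make the change in the primary models, the interim models that reuse them, and the secondary models. For the PARCA-R score, a continuous outcome, the probability boundary does not arise.

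Pre-specify what happens if the identity-link or log-link model fails to converge or gives fitted values at or above 1. One route is to fit a logistic model with the same covariates and standardise it to obtain the risk difference and risk ratio. The same rule should apply at the interim looks, so that the Z-scores compared with the limits are produced consistently. Because the trial is open-label, the wording should be settled before the first interim analysis.

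The cost is a change of analysis wording, slightly more programming and the possible need for the fallback. Minimisation, data collection and sample size do not change. The level at which the variance is clustered is a separate matter and is left as it is here.
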